## Protection of Human Subjects

### 1. Risk to the Subjects

**a. Human Subject Involvement and Characteristics.** A total of 23 individuals in stable medical condition will be enrolled in the study. Women and minorities will be recruited for this study. Children and adolescents under the age of 18 will not be enrolled.

#### Inclusion Criteria:

1. Age 18-65
2. Meet DSM-5 criteria for current CUD, provide a positive urine cannabinoid screen at baseline, self-report cannabis use within the past 30 days and using cannabis more days than not in the month preceding abstinence.
3. Meet DSM-5 criteria for bipolar I or II disorder (BD) or schizoaffective disorder, bipolar type.
4. Able to provide informed consent and read, understand, and accurately complete assessment instruments
5. Willing to commit to medication treatment and follow-up assessments
6. Prescribed daily use of at least one mood stabilizing medication (i.e., lithium, atypical antipsychotic agents, divalproex sodium / valproate, lamotrigine, carbamazepine)

#### Exclusion Criteria:

1. A primary psychiatric diagnosis other than BD (e.g., Schizophrenia)
2. Meet DSM-5 criteria for moderate or severe substance use disorder (other than nicotine or cannabis) within the past month.
3. Any uncontrolled neurologic condition (e.g., epilepsy) that could confound the results of the study
4. Any history of clinically significant brain injury
5. Any history of mental retardation, dementia, or electroconvulsive therapy in the past month
6. Any uncontrolled medical condition that may adversely affect the conduct of the study or jeopardize the safety of the subject
7. Hepatocellular disease as indicated by plasma levels of liver transaminases (aspartate transaminase, alanine transaminase) greater than 3 times the normal range
8. Reduction in creatinine clearance greater than 2 times the normal range
9. Concomitant use of medications that could interfere with glutamatergic/GABAergic transmission (e.g., benzodiazepines > 3x/week, ceftriaxone, riluzole, memantine, ketamine, topiramate, vigabatrin), due to potential confounding effects
10. Azelastine, orphenadrine, oxememazine, paraldehyde, and thalidomide are contraindicated in patients taking gabapentin; as such, individuals taking these medications will be excluded
11. Women of childbearing potential who are pregnant, lactating, or refuse adequate forms of contraception
12. Current suicidal or homicidal risk
13. Baseline scores greater than 35 on the Montgomery-Asberg Depression Rating Scale or greater than 25 on the Young Mania Rating Scale
14. Has taken gabapentin in the last 2-weeks or experienced adverse effects/allergic reaction (e.g., angioedema) from it at any time
15. Significant claustrophobia and/or past negative experiences with MRI
16. Presence of non-MRI safe materials in the body (e.g., ferrous metal implants, pacemaker)

**b. Source of Materials.** Data collected from participants will include breathalyzer readings, urine drug screens, urine biomarkers (e.g., riboflavin, ethyl glucuronide), blood chemistries, structural, functional, and neurochemical MRI brain images, and interviews and self-reports regarding substance use, psychiatric diagnoses, concomitant medications, and adverse events. To ensure confidentiality, all participant data will be number-coded, and only the investigators will have access to the master list of codes. A federal Certificate of Confidentiality, protecting participants against disclosure of sensitive information (e.g., drug use), will be obtained for the study.

**c. Compensation.** To maximize participant retention, contingency management will be applied to participant compensation such that participants will be compensated significantly more for each subsequent MRI visit they

attend (i.e., scan 1 = \$100, scan 2 = \$150), and participants will be given an additional \$50 bonus for completing both MRI visits without rescheduling and for returning their actigraphy watch. Participants will be compensated \$10/hour (rounded to the nearest half-hour) during the diagnostic visit if screened out during this time. Participants will be compensated \$50 for completing the full initial psychiatric and medical evaluation appointment. Finally, participants will be compensated \$30 for each additional non-MRI appointment (i.e., 2 total). Following the initial appointment, participants will be compensated weekly, at the end of each MRI session; \$50 of each week's compensation will be contingent on them returning their actigraphy watch to the appointment. Total compensation will thus be \$410 per participant. In our experience, this level of compensation is fair for the time commitment required without unduly coercing participants to enroll in the study despite potential concerns.

#### **d. Potential Risks**

1. Medication side effects. Gabapentin is generally well-tolerated, with sedation and dizziness being the most commonly reported side effects. Although the FDA has issued a class warning for antiepileptic drugs and suicidal thoughts and behavior, available data do not support an association between gabapentin, specifically, and increased suicidal ideation or behavior in individuals with BD or other psychiatric populations. The proposed study will minimize potential medication-related risks by implementing low starting doses and titration of study medications and will carefully monitor potential medication-related risks via biweekly scheduled visits and assessment of adverse events (including assessment of suicidal ideation and behavior at each and every study visit). The study physician will determine if the participant should be discontinued from the medication due to adverse drug reactions and will treat clinically as needed. Any confirmed incidence of serious adverse events that are deemed probably or definitely due to the study medication will result in immediate discontinuation of the study medication and follow-up assessments will be conducted until resolution. Subjects will be referred for treatment as necessary.
2. Drug interactions. Azelastine, orphenadrine, oxememazine, paraldehyde, and thalidomide are contraindicated in patients taking gabapentin; as such, individuals taking these medications will be excluded. As noted earlier, participants will be required to be taking a stable pre-existing regimen of at least one FDA-approved mood stabilizing medication treatment for BD. There are no known serious drug interactions with gabapentin and mood-stabilizing medications.
3. MRI-related risks. Individuals with non-MRI-safe medical implants or ferrous objects would be at risk for injury, if such individuals were allowed to enter the MRI scanner. Several precautions will be taken to ensure that individuals with ferrous implants or objects are not allowed to enter the MRI scanner. First, all potential participants will meet with a study physician to discuss any possible history of ferrous implants or other MRI-unsafe objects. Participants with any suspected history of ferrous implants or exposure to shrapnel will be excluded from the study. Second, participants who are deemed MRI-safe by the study physician will be screened for metal objects at the Center for Biomedical Imaging (CBI) using a handheld metal detector and a second metal detector built into the threshold of the doorway to the scanner. Participants who screen positive for metal will be asked to remove all metal objects from their person and will be rescreened. If participants continue to screen positive for metal after removing all metal objects from their person, they will be excluded from the study. Although not dangerous, participants who are claustrophobic could experience significant discomfort in the MRI scanner. As such, all participants will be assessed in terms of claustrophobia as well as past experience with MRI. Additionally, all participants will be entered into a "mock scanner" at the CBI human imaging center, which features the same dimensions of the real MRI scanner but without any of the internal machinery. Participants who report claustrophobia, past negative experience with MRI, or significant discomfort in the mock scanner will be excluded from participation. These procedures have been successfully used by our staff in previous and ongoing research studies of similar participant populations. For those participants allowed to participate in the MRI study, if abnormalities in collected brain images are found, participants will immediately be referred to an appropriate clinical care provider.
4. Cue-elicited cannabis craving. It is possible that the cannabis cue exposure functional MRI paradigm could induce cannabis craving. Participants will be asked to rate their craving from one to ten both immediately preceding and following the neuroimaging protocol. Post-scan craving ratings twenty percent above baseline will require study approved clinicians to come and speak with the patient before they are discharged. Should any craving fail to subside within 3-4 hours, participants will be provided with counseling by clinicians; appropriate referrals will be made as needed. These procedures have been successfully used by our staff in previous and ongoing research studies of similar participant populations.
5. Cannabis consumption and withdrawal. Subjects will not be required to establish abstinence at any time during the study, however, they may voluntarily attempt abstinence during the course of the study. Participants who voluntarily attempt abstinence may experience cannabis withdrawal symptoms. Study

participants will be monitored for cannabis withdrawal symptoms. Conversely, participants may continue to consume cannabis. The risks of continued cannabis use may include but are not limited to psychiatric morbidity, increased risk of traumatic injury, and other medical consequences. If in the PI's opinion a participant has significant worsening of cannabis use problems or consumption of cannabis as a result of participating in the study, the subject will be withdrawn from the study and appropriately referred.

6. **Mood destabilization.** Exacerbation of depressive or manic symptoms during the course of the study is a risk for all subjects regardless of treatment condition. We will minimize this risk by assessing mood symptoms, including suicidal ideation and behavior using the Columbia Suicide Severity Rating Scale (C-SSRS), at each and every study visit. Participants experiencing sufficient deterioration of mood stability to result in clinically significant impairment in functional capacity will be appropriately referred. Any subject exhibiting mood destabilization that is sufficient to pose an imminent danger to self or others will be hospitalized immediately and removed from the study.

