the study if the provider feels it is appropriate. Concerning the RHJVAMC, we will seek separate approval through the VAMC to post and distribute VA-approved study fliers.

Table 1. Schedule of events by study visit					
Study Visit	Visit 1 Evaluation	Visit 2 Med Disp	Visit 3 MRI	Visit 4 Med Disp	Visit 5 MRI
Clinician and PA					
Informed Consent* / HIPAA* / BrAC contract*	X				
SCID-5 (Mood/Substance)*	X				
TLFB* (90 day at V1)	X	X	X	X	X
YMRS* / MADRS* / C-SSRS*	X	X	X	X	X
BDRS / BR		X	X		X
Observe Dose (note time)		X	X	X	X
H&P* / Metal Screen*	X				
AEs / Vitals		X	X	X	X
Self-Report					
Demographics / Family history	X				
BDI* / PSQI* / BAI*	X				
BIS-11 / SPSRQ / AUDIT / ASRS / WHODAS / DSM-5 PID5/PQ	X				
BDI PW / PSQI PW / BAI PW (PW=Past Week)		X	X		X
FTND / ASRM / MCQ / CWS	X	X	X		X
Actiwatch Data Download			X	X	X
Urge to use MJ [1-10] (PRE/POST MRI)					X
Computer Tasks					
STOP-IT	X		X		X
Delay Disc	X				
GoGoNoGo Practice			X		
CNL Labs					
CMP* / CBC* / DNA*	X				
%dCDT		X			
Gabapentin level			X		X
EtG		X	X		X
Riboflavin		X	X		X
Cannabinoids/Creatinine Levels		X	X	X	X
In-House Labs					
Collect urine specimen* / UDS*	X	X	X	X	X
Breathalyzer*	X	X	X	X	X
Pregnancy Test*	X		X		X
Saliva drug screen		X	X		X

Note: "\*" Indicates assessments that must be done at Visit 1. Non-starred assessments at Visit 1 can be completed at Visit 2 if needed.

**C.2.e. Procedures.** See Table 1.

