**MRI (Visits 3, 5).** MRI visits will take place on day 5 of each condition. Participants will be asked to abstain from drugs/alcohol  $\geq 12$  hours prior to MRI. They will take their final dose of medication in front of study staff, 1 h prior to MRI, to ensure compliance. Participants who smoke will be allowed to have their last cigarette immediately prior to their final medication dose. Mood symptoms (YMRS, MADRS, C-SSRS, BDI, BAI, ASRM, PSQI), alcohol/drug/tobacco consumption (TLFB, UDS, FTND, EtG, Saliva), cannabis withdrawal (CWS), and cravings (MCQ) will be assessed. Participants will provide a urine and blood sample to test for gabapentin levels, riboflavin, liver function, and alcohol/drug consumption. Following structural and H-MRS scanning, participants will complete the CCR and go no-go fMRI tasks in counterbalanced order (see below) with the Natural Rewards Task at the end. fMRI tasks will be conducted while acquiring BOLD weighted transverse scans using a gradient-echo, echo-planar imaging (EPI) sequence: TR/TE=2200/35 ms; flip angle=90°; field of view=220x220 mm; voxel size=3.00x3.00 mm; 37 contiguous 3-mm-thick slices. Total scan time is approximately 75 m in a Siemens 3.0T Prisma (32-channel head coil). Participants will discontinue study medication following each MRI and will remain off study medication on days 6-7 of the condition. Given that the last gabapentin dose will be taken in the morning of day 5, this will provide approximately 11 half-lives of elimination prior to the start of the next condition. Crossover studies employing up to 3x the proposed dose of gabapentin have demonstrated an absence of carryover effects on clinical outcomes given the same or fewer days of washout as proposed herein. Potential carryover effects will be carefully examined using the proposed analytic design. Outside of the scanner, participants will complete the STOP-IT task. Within approximately 72 hours of day 7 of the final study condition, participants will be contacted by clinically-trained study staff to discuss adverse events, alcohol and drug consumption, and mood stability since discontinuing study medication.

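### Table 1 and the safety text disagree on whether the post-scan craving check applies at the first scan, and its 20% trigger cannot be met from a pre-scan rating of 9 or 10

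*Combined protocol and SAP*

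**What the plan says.** Item 4 of the potential risks (Protection of Human Subjects, 1.d) recognises that the cannabis cue task may provoke craving. It gives two safeguards.

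- A rating with a trigger. Participants "rate their craving from one to ten both immediately preceding and following the neuroimaging protocol", and then: "Post-scan craving ratings twenty percent above baseline will require study approved clinicians" to talk with them before they go home.
- A provision for persistent craving: "Should any craving fail to subside within 3-4 hours, participants will be provided with counseling by clinicians", with referral as needed.

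Neither safeguard is limited to a particular visit.

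The MRI paragraph of C.2.e, headed for Visits 3 and 5, says "MRI visits will take place on day 5 of each condition" and that "participants will complete the CCR and go no-go fMRI tasks in counterbalanced order". Its list of assessments at those visits names the Marijuana Craving Questionnaire (MCQ) and the Cannabis Withdrawal Scale, but not the 1-10 rating.

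In Table 1 the row "Urge to use MJ [1-10] (PRE/POST MRI" carries a single mark, under Visit 5. The row "FTND / ASRM / MCQ / CWS" is marked at Visits 1, 2, 3 and 5.

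**The concern.** The 1-10 rating is the only craving measure in the plan with a clinician action attached to a score, so two things matter: when it is taken, and whether its trigger can be reached.

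On timing, staff who work from Table 1 and the MRI paragraph would find no instruction to take the rating at Visit 3, so the check would not operate after a participant's first exposure to the cues. Staff who work from item 4 would take it at both scans.

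On the trigger, a relative rise is applied to a scale with a fixed top. The higher the starting score, the more points are needed and the fewer are available. High starting scores are plausible in this population: inclusion requires use on more days than not in the month preceding abstinence, and participants are asked to abstain for at least 12 hours before the scan.

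**Working it through.** **Timing.** The passages side by side:

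| Place | What it implies for the first scan (Visit 3) |
|---|---|
| 1.d, item 4 | Rating before and after the neuroimaging protocol; no visit excluded |
| C.2.e, MRI (Visits 3, 5) | Cue task performed; the 1-10 rating is not among the listed assessments |
| Table 1, urge row | Visit 3 cell empty; only mark at Visit 5 |

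If Table 1 is followed, 1 of 2 cue exposures per participant has no scheduled rating. If item 4 is followed, none is missed.

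Could the Visit 3 mark simply have been lost when the table was read from PDF? Nearby rows keep their Visit 3 marks: STOP-IT shows Visits 1, 3 and 5, and the go no-go practice row shows Visit 3 alone. A lost mark is unlikely but cannot be excluded.

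**Trigger.** Inputs: a scale from 1 to 10 and a rise of 20% above baseline, both from item 4. Assumptions: baseline is the pre-scan rating, and ratings are whole numbers. The first is the natural reading, because Table 1 schedules the 1-10 rating only before and after MRI.

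On a relative reading, the post-scan rating must reach 1.2 x baseline. Because item 4 does not say whether exactly 20% counts, or whether the percentage is of the score or of the scale, other readings are shown: strictly more than 20%, at least 2 points (20% of 10), and at least 1.8 points (20% of the 9-point range). The last two give identical results on whole numbers.

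| Pre-scan rating | 1.2 x rating | Lowest trigger, at least 20% | Lowest trigger, more than 20% | Lowest trigger, 2 or 1.8 points |
|---|---|---|---|---|
| 1 | 1.2 | 2 | 2 | 3 |
| 2 | 2.4 | 3 | 3 | 4 |
| 3 | 3.6 | 4 | 4 | 5 |
| 4 | 4.8 | 5 | 5 | 6 |
| 5 | 6.0 | 6 | 7 | 7 |
| 6 | 7.2 | 8 | 8 | 8 |
| 7 | 8.4 | 9 | 9 | 9 |
| 8 | 9.6 | 10 | 10 | 10 |
| 9 | 10.8 | none | none | none |
| 10 | 12.0 | none | none | none |

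The choice of reading changes what is needed at baselines 1 to 5. It makes no difference at 9 and 10, where the trigger cannot fire under any of the four. If fractional ratings were allowed, the highest baseline from which the at-least-20% rule could fire would be 10 / 1.2 = 8.33.

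Under the at-least-20% reading, a move from 1 to 2 requires a clinician contact, while a move from 9 to 10 does not.

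**The case against.** Three stronger conclusions are tempting, and the documents support none of them.

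A reader might infer that the plan intends to skip the check at the first scan. Only Table 1 points that way. Item 4 ties the rating to the neuroimaging protocol without restriction, and the table was machine-read. This is a contradiction between schedule and text, not a settled decision.

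A reader might infer that participants with the strongest craving have no protection. The 3-4 hour provision covers any craving, whatever the starting score, and does not depend on the 20% trigger. It is also fair to say that the trigger is meant to detect a rise caused by the scan. Someone who scores 10 before and after shows no measurable rise, so the only whole-number rise that the ceiling hides is 9 to 10. What remains is narrower. These participants lose the automatic contact before discharge, and the documents do not say who follows craving over the 3-4 hours or how. The one contact described after the final condition, within about 72 hours of its day 7, covers adverse events, substance use and mood; craving is not named.

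A reader might infer that a Visit 5-only rating leaves no within-person comparison of urge between gabapentin and placebo. It does not. The cue task collects an urge rating from 0 to 4 after each block at both scans, and the MCQ is scheduled at Visits 3 and 5. The 1-10 rating is presented as a safety step, so there is no case for demanding a paired analysis of it. Neither of the other measures has a clinician action attached, however, so they do not stand in for the safety check.

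**Conclusion.** The point holds in two limited parts. First, the schedule and the safety text contradict each other on whether the craving check applies at the first scan; 1 of 2 cue exposures per participant is affected if Table 1 is followed. This rests on the Visit 3 cell being truly empty, which is likely but not certain. Second, the trigger does not fit its own scale: it cannot be met from 9 or 10, given that baseline means the pre-scan rating. That result does not depend on which of the four readings of twenty percent is taken. The number of participants concerned is unknown, because the documents give no distribution of pre-scan ratings. No sample size, power or efficacy analysis is touched. The matter is worth correcting because a safeguard the protocol promises may not operate as written, and the correction is cheap.

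**What to change.** 1. Reconcile Table 1, the MRI paragraph of C.2.e and item 4 of the potential risks, so that all three state the same thing about which scans carry the 1-10 rating.
2. Define baseline in item 4, and say whether the percentage refers to the starting score or to the scale and whether exactly 20% counts.
3. Have the study clinicians reconcile the trigger with the 10-point ceiling, and state how the 3-4 hour provision is followed up. The threshold and the clinical rule are theirs to set; none is proposed here.

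The cost is small: a table cell or a qualifying phrase, and a few sentences in the safety text. If the reconciliation leads to a rating at a further scan, that would add about a minute per participant (an estimate, not a figure from the documents) and possibly a few clinician contacts.

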## **2. Adequacy of Protection Against Risks**

**a. Recruitment and Informed Consent.** Recruitment will occur by clinical referral, response to advertisements and flyers, and chart review. The principal investigator, the study coordinator, co-investigators with completed masters-or-higher-level clinical training will obtain informed consent. At the screening visit, potential participants will be provided a copy of the IRB-approved consent document to review. After providing the participant with time to read the consent, the principal investigator, the study coordinator, co-investigators with completed masters-or-higher-level clinical training will review the consent document page by page with the participant and answer any questions. Only then will the participant be asked to sign the consent document. Participants will be given a copy of the signed consent document. The entire informed consent process will be documented in the research progress notes. The signed, original consent document will be maintained in the participant source record with a copy of the consent binder located at the Addiction Sciences Division, Department of Psychiatry and Behavioral Sciences, Medical University of South Carolina.

**b. Safety Assessments.** At every visit, clinically-trained study staff will evaluate subjects' manic and/or depressive symptoms, including suicidal ideation. Mood symptoms will also be quantified using standardized instruments including MADRS, YMRS, BDI-II, and BAI. Adverse events will be assessed at every study visit.

### **c. Protection Against Risk.**

**Psychiatric Risks.** The investigative team has a great deal of experience working with the study population and have the resources to make appropriate referrals as needed. Psychiatric symptoms will be assessed on a biweekly basis by standardized assessments and by clinical interview. Participants scoring >4 on the suicide item (item 4) of the MADRS; endorsing items 4 ("Have you had these [suicidal] thoughts and some intention of acting on them?"), 5 ("Have you started to work out or worked out the details of how to kill yourself? Do you intend to carry out this plan?"), or 6 ("Have you done anything, started to do anything, or prepared to do anything to end your life?") on the C-SSRS, or otherwise exhibiting potentially life-threatening decompensation in mood or other psychiatric symptoms at any study visit will be removed from the study and referred for outpatient or inpatient treatment as necessary.

**Medical Risks.** Gabapentin is excreted by a renal route. A blood chemistry panel will be performed and reviewed by the study physician prior to beginning the study medication. Participants with clinically significant renal, or hepatic (transaminases elevated > 3 times normal), insufficiency will not be eligible to participate in the study. Subjects will be referred for treatment as necessary.

**MRI Risks.** The investigative team has a great deal of experience with human MRI research and [name] is a core faculty member of the CBI at MUSC. MRI safety and comfort will be assessed at baseline and at each MRI visit. Participants with non-MRI-safe medical implants or ferrous objects will be excluded from participation as will individuals evidencing significant discomfort with MRI.

**Pregnancy.** Gabapentin is rated as a Category C medication in terms of pregnancy. Because there are no adequate controlled studies of gabapentin in pregnant women, it is unknown whether the drug can cause fetal harm or affect reproductive capacity in humans. Therefore, women of childbearing potential must agree to pregnancy testing and use of adequate contraception in order to be eligible to participate in the study. Females will be given a urinary pregnancy test at the screening visit and weekly thereafter. Any female participant who becomes pregnant during the study will be discontinued from the study medication and removed from study participation. For all included females of childbearing potential, current forms of birth control and date of last menstruation will be assessed at each study visit.

Confidentiality. Records with identifying information (e.g., consent documents) will be stored in a locked file. All other non-MRI participant data will be collected via direct data capture (REDCap); MRI data will be automatically transferred to Linux-based servers managed by CBI. Both MRI and non-MRI data will be stored in restricted access directories on password-protected, encrypted servers managed by CBI and the Department of Psychiatry and Behavioral Sciences at MUSC. Participants will be given an ID number for all MRI and non-MRI data files. The master list of codes will be accessible only to the investigators, and will be stored in a locked office. As noted above, a federal Certificate of Confidentiality, protecting participants against disclosure of sensitive information (e.g., drug use), will be obtained prior to study initiation.

Emergencies. All study participants will be instructed how to access the 24-hour on-call system available at the Medical University of South Carolina. In the event that a participant experiences an adverse event after hours, s/he will be instructed to access the 24-hour on-call service. If it is determined that the participant needs immediate help, the participant may be advised to immediately go to the emergency room. In that event, proper medical treatment will be administered, per ER procedures. [name] and [name] will be available by pager/cell as necessary. The Investigational Drug Service (IDS) will be available 24 hours/day, 7 days/week for emergency identification of treatment group assignment and unblinding as necessary.

Substance Abuse Treatment. Subjects may receive additional non-pharmacologic substance abuse treatment during study participation. Attendance at group-based recovery activities (e.g., Narcotics Anonymous) will be encouraged and monitored.

